Suppose 80% of patients (n=536) enrolled will have a bone marrow sample available for E-selectin analysis. Assuming 375 patients (out of 536 patients) achieving a remission, we will have 88% power to detect an effect size of 0.3 (effect size defined as the difference in mean divided by the standard deviation,  $\delta = |\mu_1 - \mu_2|/\sigma$ ) in baseline E-selectin expression levels between the responders and non-responders at the 0.05 two-sided alpha level; this assumes a remission rate of 70%. Furthermore, to analyze multiple factors related to the probability of achieving CR, logistic regression models will be constructed. For DFS, EFS, and OS, E-selectin level along with other potentially prognostic factors will be examined in multivariable analyses, using Cox regression model, stratified by treatment arm. Similar analyses will be conducted for sE-selectin. Secondary analysis will evaluate the sE-selectin expression level pre- vs. post-induction will be compared using two-sample t-tests or Wilcoxon rank-sum tests, as well as descriptive statistics and graphical methods. Exploratory analysis will be conducted to investigate the optimal cut-point of baseline E-selectin expression level through ROC analysis.

Flow cytometry will be used to assess for MRD by discriminating between normal regenerating hematopoietic cells in the bone marrow and any remaining acute myeloid leukemia (AML) which abnormally expresses cell surface antigens [27]. This technique, termed “Difference from Normal” is based on correlating the quantitative expression of multiple cell surface antigens (gene products) in the specimens using standardized antibody panels. The Difference from Normal approach identifies all the normal regenerating cells within the specimen first, subtracts them away and then detects clusters of abnormal cells within the remaining data set. Using this technique, it is possible to define the precise composition of the specimen, identifying cells of all lineages and maturational stages as well as assessing specimen quality in addition to detecting and quantifying any abnormal cell population [28].

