#### 14.3.4 Statistical Analysis Plan

A041701 is a randomized Phase II/III study. The study will open with accrual open to two arms (one experimental arm and one control arm). The total Phase II sample size is

expected to be approximately 262 eligible patients (131 patients per arm). The total Phase III sample size is expected to be 670 (335 patients per arm). In the event that the Alliance Data Safety and Monitoring Board (DSMB) releases the requested Phase II data, the hypothesis-generating analyses described here will be performed based on Phase II accrual. Otherwise, this proposal is mainly based on Phase III accrual. Because this substudy is being newly incorporated in a protocol amendment post-study activation (54 patients accrued as of 11/22/2019), the current accrual rate suggests that approximately 600 evaluable Phase III patients may participate in this substudy.

We assume that 60% patients treated on A041701 will achieve a CR/CRi. Of those achieving CR/CRi, we expect to have end-of-induction marrow samples for MRD assessment on 90% of patients (n=324), and blood samples on 95% of patients (n=342).

We note that the Cox regression models below will be stratified by treatment arm as appropriate. Multivariable analyses will be evaluated as a complement to each univariate analysis. Multivariable analyses will include baseline covariates age, gender, performance status, cytogenetic risk, white blood cell count, platelet count, bone marrow blast percentage, and number of induction courses (1 vs 2).

*1. Primary integrated objective (To evaluate whether the presence of MRD will be a strong predictor of relapse-free survival (RFS) in patients achieving a CR/CRi following induction chemotherapy):*

We expect that approximately 25% of patients who achieve a CR/CRi will have detectable MRD by flow cytometry using the current methodology. Log-rank test will be used to assess associations between MRD and RFS. And RFS will be estimated by the Kaplan-Meier method.

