In the calculations below, the RFS is assumed to follow an exponential distribution with a median of 11.5 months (null hypothesis). For the RFS outcome (assuming 59 months of accrual and an additional one year of follow-up per protocol), the marrow results (n=324) will have 80% power to detect an absolute difference in median RFS of 5 months between MRD- and MRD+ patients (HR = 0.7), 13 months for MRD- versus 8 months for MRD+ with a two-sided alpha of 0.05, and the blood (n=342) results will have 83% power for the same effect size and alpha level. C-statistics will be calculated to quantify the model's ability to predict outcomes. We will also fit multivariable Cox regression models with both end-of-induction MRD (present vs absent) plus the covariates listed above.

In the event that the Alliance Data Safety and Monitoring Board (DSMB) releases the requested Phase II data, the hypothesis-generating analyses described here will be performed based on Phase II accrual. Similarly, because this substudy is being newly incorporated in a protocol amendment post-study activation (54 patients accrued as of 11/22/2019), the current accrual rate suggests that approximately 200 evaluable Phase II patients may participate in this substudy.

For the RFS outcome (assuming additional 18 months of accrual and an additional one year of follow-up per protocol), the marrow results (n=108) will have 63% power, and the blood (n=114) results will have 65% power for a HR of 0.6 and two-sided alpha of 0.05. C-statistics will be calculated to quantify the model's ability to predict outcomes. We will also fit multivariable Cox regression models with both end-of-induction MRD (present vs absent) plus the covariates listed above.

*To analyze the association of MRD with overall survival (OS), time-to-relapse (TTR, defined as the time from randomization to relapse, with death without relapse censored at time of death), and relapse risk: OS and TTR will be estimated using the Kaplan-Meier*

method, and compared using log-rank tests. Risk of relapse (RR) will be summarized using cumulative incidence estimates. Cox regression analyses will be used to assess the association between the outcomes of interest and the covariates listed above.

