*To compare whether evaluate whether MRD from the peripheral blood provides similar prognostic information compared to bone marrow:* We will fit multivariate marginal Cox regression models (Wei, Lin, Weissfeld 1989) including either blood and marrow MRD results with covariates for sample type (blood versus marrow), and a second model both blood and marrow MRD, and a third model with the interaction between the two covariates. We will calculate C-statistics for each of these models.

*To compare the presence of MRD at the end of induction versus end of consolidation time points to determine if either of these better predicts RFS:* We will fit multivariate marginal Cox regression models (Wei, Lin, Weissfeld 1989) including either MRD results at the end of induction or at the end of consolidation. We will calculate C-statistics for each of these models.

*To compare the rates of MRD by treatment arm:* Two-way table and chi-square tests will be used to compare the MRD rates by treatment arm.

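### The E-selectin substudy plans only same-data C-statistics and an unvalidated ROC cut-point, so the reported performance of its multi-parameter models will be too high

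*Combined protocol and SAP*

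**What the plan says.** Section 14.3.4 gives the power for MRD against relapse-free survival twice, once for the Phase III and once for the Phase II sample. Each time it continues that "C-statistics will be calculated to quantify" how well the model predicts. The next sentence adds Cox models with MRD and a covariate list: "Multivariable analyses will include baseline covariates age, gender, performance status, cytogenetic risk, white blood cell count, platelet count, bone marrow blast percentage", plus the number of induction courses. That is eight covariates, so at least nine parameters with MRD.

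C-statistics return in the same section for two comparisons: blood against marrow MRD (models with one source, with both, and with their interaction), and end of induction against end of consolidation. The instruction is: "We will calculate C-statistics for each of these models".

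Section 14.3.3 says of the flow-cytometry marker: "Exploratory analysis will be conducted to investigate the optimal cut-point of baseline E-selectin expression level through ROC analysis". The tests it specifies (t-test or Wilcoxon, logistic and Cox regression) use the E-selectin level, not a dichotomised marker.

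No resampling, split sample, outside validation or cut-point correction appears anywhere. The error-rate rule for correlative studies in section 14.1.4 deals with the number of hypotheses, which is a different matter. Sections 13.1.2 and 13.2.1 record that, from Amendment 04, there is no further Phase III accrual, so the Phase II projection in section 14.3.4 is the one that now applies.

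**The concern.** A C-statistic computed on the patients who supplied the coefficients measures fit as well as prediction. The excess grows with the number of parameters per event, and the plan would put at least nine parameters on roughly 72–76 events. A model with no predictive value would then report a C visibly above 0.5. Where C is used to choose between models of different size, the larger one starts with an advantage.

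A cut-point picked to maximise separation has the same problem: sensitivity and specificity at that cut are the best of many tries. Any p-value computed there as if the cut had been fixed in advance would be too small.

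At stake is how the MRD and E-selectin results are read by those planning later studies. The trial's treatment comparison does not depend on them.

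**Working it through.** **Inputs from the plan (14.3.3, 14.3.4).** "approximately 200 evaluable Phase II patients may participate in this substudy"; "We assume that 60% patients treated on A041701 will achieve a CR/CRi"; "end-of-induction marrow samples for MRD assessment on 90% of patients (n=324), and blood samples on 95% of patients (n=342"). Also: 25% MRD-positive, hazard ratio 0.6 (Phase II) or 0.7 (Phase III), 13-month median for MRD-negative patients, 18 months of further accrual plus 12 months of follow-up for Phase II and 59 plus 12 for Phase III. For E-selectin: 80% of 670 = 536 patients, 375 with remission.

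**Step 1: the plan's own figures.**
- Marrow: 200 × 0.60 × 0.90 = 108. Blood: 200 × 0.60 × 0.95 = 114. Both match.
- E-selectin: z = 0.3 × √(375 × 161 / 536) = 3.18; 3.18 − 1.96 = 1.22, power 0.89 against a stated 88%. This agrees within rounding.
- The plan gives no figure for C or its bias, so these were simulated.

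**Step 2: bias in C.** Survival was exponential, with censoring uniform over 12–30 months (n = 108) or 12–71 months (n = 324). Optimism = C in the fitting data − C of the same coefficients in new patients. In the three-term model, blood MRD copies marrow MRD with probability 0.8 and is otherwise an independent 25% draw; only marrow MRD affects the hazard. The prognostic-covariate rows give three standard-normal covariates a log hazard of 0.15 or 0.30 per SD, in addition to the MRD effect. These settings are assumptions.

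| Model | n | True effect | C, fitting data | C, new patients | Optimism |
|---|---|---|---|---|---|
| MRD alone | 108 | none | 0.52 | 0.50 | 0.02 |
| MRD alone | 108 | MRD 1/0.6 | 0.549 | 0.546 | 0.003 |
| Three-term | 108 | none | 0.536 | 0.500 | 0.036 |
| Three-term | 108 | MRD 1/0.6 | 0.561 | 0.543 | 0.018 |
| Nine-parameter | 108 | none | 0.601 | 0.499 | 0.102 |
| Nine-parameter | 108 | MRD 1/0.6 only | 0.614 | 0.530 | 0.084 |
| Nine-parameter | 108 | MRD + covariates, 0.15 | 0.632 | 0.564 | 0.068 |
| Nine-parameter | 108 | MRD + covariates, 0.30 | 0.673 | 0.622 | 0.051 |
| Nine-parameter | 324 | none | 0.55 | 0.50 | 0.05 |
| Nine-parameter | 324 | MRD 1/0.7 + covariates, 0.15 | 0.597 | 0.571 | 0.026 |
| Nine-parameter | 324 | MRD 1/0.7 + covariates, 0.30 | 0.649 | 0.634 | 0.015 |

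**Step 3: effect on model comparison.** With a true marrow-MRD effect and n = 108, the three-term model beats MRD alone in the fitting data by 0.561 − 0.549 = 0.012. In new patients the difference is 0.543 − 0.546 = −0.003, that is, no gain. These come from separate simulation runs, so only the direction matters.

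**Step 4: cut-point.** A marker unrelated to a 70% remission rate was cut where sensitivity + specificity − 1 is largest, then tested by an uncorrected chi-square test at 0.05. False-positive rates were:
- search over all values or the middle 80%: about 41% at n = 536, and 38–41% at n = 210 or 160;
- search limited to the middle 50%: about 27–30%.

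The plan states no Phase II E-selectin sample. The values 210 (0.8 × 262) and 160 (0.8 × 200) are assumptions.

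**Step 5: do the remedies work?** Corrected C = apparent C − mean over resamples of (C in the resample − C of the resample's coefficients in the full data). For the nine-parameter model at n = 108:
- no effect: 0.601 corrected to 0.531 (new patients 0.499);
- MRD only: 0.614 corrected to 0.553 (new patients 0.530).

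The correction therefore removes 0.070 of 0.102 and 0.061 of 0.084. A permutation test of the selected cut gave false-positive rates of 5.6% (n = 210) and 4.1% (n = 536).

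**The case against.** The strongest reply is that the plan does less than the criticism implies, and much of that stands.

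- **Which model the C-statistic belongs to.** The sentence comes before the multivariable models, which are introduced as an addition. Read that way it concerns MRD alone, where the bias is negligible to small. The text is ambiguous, so the larger bias applies only where C is reported for a multi-parameter model. The comparison of induction with consolidation MRD uses models of equal size, so the bias should largely cancel there. Neither answer covers the blood, marrow and interaction comparison.
- **Significance.** A reader might infer that a useless marker will often be declared significant. The documents do not support this, because no test of the dichotomised marker is planned. The 27–41% is conditional on someone adding one.
- **Sample size.** It is tempting to blame the small Phase II sample for both problems. That is right for C. The cut-point analysis was written for 536 patients, and its inflation is about the same there.
- **Near-chance prediction.** One might conclude that true performance would be close to 0.5. That needs covariates without prognostic value, whereas section 14.1.1 treats cytogenetics, one of the listed covariates, as a leading prognostic factor.
- **Labels.** Section 14.3.2 calls the objectives exploratory, 14.3.3 calls the cut-point search exploratory, and 14.3.4 calls the Phase II-based analyses hypothesis-generating. No document says that a threshold will be carried forward. This limits the harm. It does not correct a biased number, and section 14.3.4 also presents MRD prediction as its primary integrated objective.

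**Conclusion.** The point holds for multi-parameter models and, conditionally, for the cut-point. Sections 14.3.3 and 14.3.4 plan only apparent performance. At n = 108 this overstates C by about 0.05–0.10 for MRD plus eight covariates, and by 0.02–0.04 for the three-term model, which tilts that comparison toward the larger model. For MRD alone the bias is 0.003–0.02 and needs no action. An uncorrected test at the ROC-selected cut would have a false-positive rate of about 27–41%, depending mainly on the range searched.

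The C figures rest on exponential survival, the plan's accrual and follow-up, and assumed covariate distributions and effects. The cut-point figures rest on a 70% remission rate and, below 536, on assumed sample sizes. This is a reporting and method weakness in an exploratory substudy. It is worth correcting because a better method is readily available, and it has no bearing on the EFS or OS conclusions.

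**What to change.** **Section 14.3.4.** State which models the C-statistics refer to. For every model with more than one parameter, report the bootstrap optimism-corrected C, repeating all modelling steps in each resample, and base the blood, marrow and interaction comparison on the corrected values. The apparent C can be shown beside it. Note that the correction is partial: in Step 5 about 0.02–0.03 of optimism remained.

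**Section 14.3.3.** Keep the continuous E-selectin level as the main analysis. Label any ROC cut-point as unvalidated and give cross-validated sensitivity and specificity. If the cut is tested, use a permutation (maximally selected) p-value. A borrowed threshold is not a ready substitute: the highest-quartile split in section 14.3.1 was for FUT7 RNA expression against 5-year survival, and the documents give no basis for applying it to a flow-cytometry measure compared by remission status.

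**Cost.** A little more analysis code and a lower reported C. No new data are needed, and trial conduct does not change.

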#### 6.2 Specimen collection and submission

The Alliance A041701 Correlative Science Manual (CSM) contains instructions for specimen collection, processing and shipping. The manual can be found on the BioMS and CTSU websites. Questions regarding the CSM should be addressed to the contacts specified in the manual.

For all patients registered to Alliance A041701: Bone marrow and peripheral blood will be collected and banked for molecular genetic analysis described in [Section 14.2](#).

For patients registered to substudy A041701-LC1 and/or patients who consent to banking: All participating institutions must ask patients for their consent to participate in Alliance A041701-LC1 and the banking of their specimens for future studies, although patient participation is optional. Rationale and methods for the scientific components of these studies are described in Section 14.0. For patients who consent to participate, bone marrow and blood samples will be collected at the following time points for these studies:

	At Pre-registration	End of Induction	End of Consolidation	Relapse	Storage/Shipping conditions	Submit to:
For all patients registered to A041701, submit the following						
Bone marrow aspirate (EDTA/lavender top)	5 mL				Ambient	HEME
Peripheral blood (EDTA/lavender top)	10 mL				Ambient	HEME
For patients registered to A041701-LC1A, submit the following						
Bone marrow aspirate (heparin/green top)	2 mL	2 mL	2 mL		Ambient	Hematologics
Peripheral blood (Na citrate/light blue top)	2.7 mL	2.7 mL			Frozen/dry ice	HEME

For patients who consent to banking B , submit the following						
Bone marrow aspirate (EDTA/lavender top)	5 mL	5 mL	5 mL	5 mL	Ambient	HEME
Peripheral blood (EDTA/lavender top)	10 mL	10 mL	10 mL	10 mL	Ambient	HEME

- 1 Or submit 30 mL peripheral blood (EDTA/lavender top) if marrow inaspirable or if the patient has had a bone marrow aspiration prior to pre-registration and refuses to have another one performed. This peripheral blood is in addition to the 10 mL required prior to treatment.

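### The 63% and 65% powers given for the Phase II-based MRD analysis do not follow from the 18 + 12 months of follow-up stated with them; those inputs give about 50-55%

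*Combined protocol and SAP*

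**What the plan says.** Section 14.3.4 (Statistical Analysis Plan for A041701-LC1) gives two power calculations for MRD after induction as a predictor of RFS. The one at issue applies if the DSMB releases Phase II data. Its inputs are:

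- **Test:** "Log-rank test will be used to assess associations between MRD and RFS".
- **Group split:** "We expect that approximately 25% of patients who achieve a CR/CRi will have detectable MRD".
- **RFS distribution:** exponential with median 11.5 months, labelled the null hypothesis. The section does not say whether this is the overall median or that of one MRD group.
- **Time:** "assuming additional 18 months of accrual and an additional one year of follow-up per protocol".
- **Result for marrow:** "the marrow results (n=108) will have 63% power".
- **Result for blood:** "the blood (n=114) results will have 65% power for a HR of 0.6 and two-sided alpha of 0.05".

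The sample sizes come from about 200 evaluable Phase II patients, 60% CR/CRi, and samples from 90% (marrow) or 95% (blood) of those in remission. No expected number of RFS events is given. The Phase III-based calculation in the same section states 80% (n=324) and 83% (n=342) at a hazard ratio of 0.7.

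**The concern.** Log-rank power depends on the number of events, not on the number of patients. With a median of 11.5 months and each patient observed for 12 to 30 months, a sizeable share of patients would still be event-free at analysis. A power that matches a count of 108 events in 108 patients is therefore suspect.

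The point has some current relevance. Amendment 04 ended accrual whatever the Phase II result, so the 600-patient version of this analysis cannot take place. Section 13.5 says release of the EFS and OS outcome data will be requested. If they are released, the Phase II-based sentence is the only applicable power statement for what Section 14.3.4 calls its primary integrated objective. Someone interpreting a non-significant MRD result would rely on it.

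**Working it through.** **Formula.** Schoenfeld power = Φ(|ln HR| × √(p(1−p)d) − 1.960), with p = 0.25, so p(1−p) = 0.1875, and d = events. |ln 0.6| = 0.5108.

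**Step 1: sample sizes.** 200 × 0.60 × 0.90 = 108 and 200 × 0.60 × 0.95 = 114. Both reproduce.

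**Step 2: the stated powers, with d = n.**

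- Marrow: 0.5108 × √(0.1875 × 108) − 1.960 = 2.299 − 1.960 = 0.339, power 63.3% (stated 63%).
- Blood: 0.5108 × √(0.1875 × 114) − 1.960 = 2.362 − 1.960 = 0.402, power 65.6% (stated 65%).
- The same all-events formula at hazard ratio 0.7 gives 79.4% (n=324, stated 80%) and 81.5% (n=342, stated 83%).

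**Step 3: events under the stated follow-up.** With uniform accrual over A = 18 months, minimum follow-up F = 12 months and λ = ln 2 / 11.5 = 0.0603:

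P(event) = 1 − [exp(−λF) − exp(−λ(A+F))]/(λA) = 1 − (0.485 − 0.164)/1.085 = 0.704.

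That is 108 × 0.704 = 76 events for marrow and 114 × 0.704 = 80 for blood. Splitting the groups so that the overall median stays at 11.5 months (13.1 months MRD-negative, 7.9 MRD-positive) gives almost the same counts, 75.5 and 79.7.

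**Step 4: power with those events, hazard ratio 0.6.**

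- Marrow: 0.5108 × √(0.1875 × 76) − 1.960 = −0.03, power about 49%. Log-rank simulation gives 53-54%.
- Blood: 0.5108 × √(0.1875 × 80) − 1.960 = 0.02, power about 51%. Simulation gives 55%.

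The formula is somewhat conservative with a 25:75 split, so both methods are shown.

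**Step 5: which group has the 11.5-month median (marrow, n=108).**

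| Reading of 11.5 months | Events | Power, formula to simulation |
|---|---|---|
| Overall | 76 | 49-54% |
| MRD-negative | 80 | 51-56% |
| MRD-positive | 61 | 41-47% |

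No reading reaches 63%. By the formula, 63% needs about 107 events: 0.5108 × √(0.1875 × 107) − 1.960 = 0.33, power 63%.

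**Step 6: longer follow-up (overall median 11.5, 18 months of accrual).**

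| Minimum follow-up | Events, marrow | Power, marrow (simulation) |
|---|---|---|
| 12 months | 76 | 53-54% |
| 24 months | 92 | 59-60% |
| 39 months | 101 | about 63% |

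At 39 months blood has about 106 events and simulated power of about 64%. The 39 months is an assumption, because the documents do not give the end of accrual. Section 14.3.4 counts 54 patients on 11/22/2019; adding its 18 months gives about May 2021, some 39 months before the August 12, 2024 lock.

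**Step 7: detectable effect.** With 76 events and 80% power, HR = exp(−(1.960 + 0.842)/√(0.1875 × 76)) = exp(−0.742), between 0.47 and 0.48.

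**The case against.** The strongest reply is that the one-year follow-up assumption is out of date. Amendment 04 sets the lock at August 12, 2024 and cites mature follow-up in Section 13.2.1. If accrual ended about May 2021, marrow power at the lock is about 63%, which is the stated figure. This stands as far as it goes. A reader might infer from 49-54% that the analysis will have only even odds of detecting a hazard ratio of 0.6; the documents do not support that, because the lock date points to longer follow-up. The reply does not rescue the sentence, which attributes 63% to one year of follow-up.

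Three other stronger readings also go too far:

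- **That the plan counted every patient as an event.** This is an inference, since no event count or method is given. Other settings also reproduce the Phase II pair with censoring: a 1:1 split with MRD-negative median 13 months (62.9% and 65.3%), or a one-sided 0.05 test with MRD-negative median 11.5 (63.2% and 65.2%). Both contradict stated inputs and fit the Phase III-based pair less well (85% and 87%, or 83% and 85%, against 80% and 83%), so omitted censoring is the likelier explanation but is not proven.
- **That power at a hazard ratio of 0.7 is misstated too.** The Phase II-based sentence claims power only at 0.6.
- **That n should shrink by the 80% sample availability in Section 14.3.3.** That rate concerns marrow for the E-selectin assay. The 108 already includes 90% availability for MRD, so applying both stacks two rates. Participation in LC1 is voluntary ("although patient participation is optional" in Section 6.2), which is a reason to use the actual number.

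Finally, Section 14.3.2 lists these objectives as exploratory and Section 14.3.4 calls the Phase II-based analyses hypothesis-generating. No trial decision depends on them, and the plan already discloses power well below 80%.

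**Conclusion.** The point holds as an internal inconsistency of minor severity. Under the section's own inputs, the Phase II-based powers should be about 49-54% rather than 63% for marrow, and about 51-55% rather than 65% for blood. That is a shortfall of roughly 9 to 14 points.

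The ranges rest on uniform accrual, exponential RFS, 25% MRD-positive and 11.5 months as the overall median. Reading the median as that of one MRD group widens the marrow range to about 41-56% without reaching 63%. Omitted censoring is a plausible cause, not an established one. Power at the actual lock may come close to the stated values, but that depends on an accrual end date the documents do not give.

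**What to change.** Correct the Phase II-based sentence in Section 14.3.4 so that events, follow-up and power agree. Either of these would do:

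1. Keep 18 + 12 months and state about 76 events (marrow) and 80 events (blood), with about 50-55% power at a hazard ratio of 0.6.
2. Recalculate with the follow-up available at the August 12, 2024 lock and the LC1 participation actually obtained. This is preferable, because it describes the analysis that will be done. As a guide at n=108, marrow power is about 59-60% with 24 months' minimum follow-up and about 63% with 39 months.

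In both cases, say which group has the 11.5-month median and add the hazard ratio detectable with 80% power (just under 0.48 at 76 events).

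The cost is one corrected sentence and a short calculation. Nothing changes in the design, the treatment, the trial's primary endpoints or the data collected. Under the first option the stated power becomes less favourable.

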### 7.1 Arm 1 Treatment: 7+3

#### 7.1.1 Remission Induction

- Daunorubicin 60 mg  $\text{m}^2/\text{day}$  IV Days 1-3 (total dose 180 mg/ $\text{m}^2$ )
- Cytarabine 100 mg/ $\text{m}^2/\text{day}$  CIVI Days 1-7 (168 hour infusion, total dose 700 mg/ $\text{m}^2$ )

During the Remission Induction, a bone marrow examination (aspirate and biopsy) on Day 14 (+3 days) is required in all patients. Recommendations regarding the need for second induction are provided in the table below. Consult with the study chair if there are questions about the need for reinduction,

Bone Marrow Cellularity	Bone Marrow Leukemic Blasts	Action
$\geq 20\%$	$\geq 5\%$	Second remission induction
	$< 5\%$	Do not start second remission induction therapy. Repeat bone marrow biopsy upon count recovery or by Day 42
$< 20\%$	$\geq 5\%$	Repeat bone marrow biopsy in one week, and follow guidelines in table.

	< 5%	Do not start second remission induction therapy. Repeat bone marrow biopsy upon count recovery or by Day 42
--	------	---

Patients with residual disease as indicated above on Day 14 or subsequent biopsy following the first course of induction chemotherapy are eligible to receive a second remission induction course. It is recommended that a second induction course start within 7 days of bone marrow documentation of residual disease but may be delayed based on the clinical status of the patient. Removal of a patient following a single cycle of induction chemotherapy to receive non-protocol therapy is highly discouraged as the results of the day 14 bone marrow (i.e. high cellularity, blast percentage) do not predict the outcome of second remission induction course.

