Bone marrow specimens will be obtained at the end of induction and the end of consolidation. The quality of each specimen will be defined based on total cellularity, hemodilution, and viability. Collection of fewer than 100,000 cells in each of 8 tubes, significant hemodilution of >50%, lymphoid predominance of >50%, or significant cell death resulted in a specimen quality classification of suboptimal or inadequate [29].

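### Exploratory MRD analyses: the time-to-relapse Kaplan-Meier curve is not a relapse probability, and its clock starts before MRD status is known

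*Combined protocol and SAP*

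**What the plan says.** Section 14.3.4 analyses MRD against OS, TTR and relapse risk. TTR is "defined as the time from randomization to relapse, with death without relapse censored at time of death". For estimation, "OS and TTR will be estimated using the Kaplan-Meier" method, with log-rank tests for the comparison. The next sentence treats a separate quantity: "Risk of relapse (RR) will be summarized using cumulative incidence estimates". Cox regression follows. Number of induction courses (1 or 2) is among the covariates of the multivariable models only.

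On when MRD is known, Section 14.3.3 says "Bone marrow specimens will be obtained at the end of induction and the end of consolidation". The end-of-induction analysis is confined to patients in CR/CRi with a sample. After a first induction that needs no second course, the instruction in Section 7.1.1 (repeated for Arm 2 in Section 7.2.1) is "Repeat bone marrow biopsy upon count recovery or by Day 42". A second induction pushes the assessment later.

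No landmark, delayed entry or remission-based origin is given for TTR. By contrast, DFS in Section 13.2.2 starts at CR/CRi.

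**The concern.** There are two separate issues.

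**Competing risk.** Kaplan-Meier with deaths censored estimates what relapse would look like if death in remission could not happen. Patients here are 60 or older, and Section 1.5 itself cites non-relapse mortality when arguing for EFS over CR. If the curve is read as the chance of relapse, it is too high, and in the illustration below more so in the group with the faster event rate. The displayed gap between MRD groups then widens as well.

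**Time origin.** The grouping factor is measured after the clock starts. Every patient in the analysis must have survived, responded and been sampled, so the time from randomization to the sample is event-free by construction. If that interval is longer for MRD-positive patients, for example because more of them needed a second induction, they are credited with more guaranteed relapse-free time and the MRD effect looks weaker than it is.

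What is at stake is how an exploratory prognostic result is read. No treatment comparison is involved.

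**Working it through.** **Inputs from Section 14.3.4.** About 600 substudy patients, 60% reaching CR/CRi, marrow in 90% and blood in 95% of those; "approximately 25% of patients who achieve a CR/CRi will have detectable MRD by flow cytometry"; median RFS "13 months for MRD- versus 8 months for MRD+ with a two-sided alpha of 0.05"; 59 months of accrual plus 12 of follow-up.

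**Plan figures.** The plan gives no rate or power for TTR, so there is none to reproduce. The sample sizes do reproduce: 600 × 0.60 × 0.90 = 324 and 600 × 0.60 × 0.95 = 342. The medians also fit the plan's overall median of 11.5 months: 0.75 × 2^(−t/13) + 0.25 × 2^(−t/8) = 0.5 at t = 11.45. The plan pairs these medians with a hazard ratio of 0.7, although 8/13 = 0.615; that is a separate matter, and the medians are used here.

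**Assumptions not in the documents.** A share q of RFS events are deaths without relapse, the same in both MRD groups; hazards are constant; time runs from the MRD assessment.

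**Step 1: Kaplan-Meier against cumulative incidence.** With λ = ln 2 / median:

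- one minus Kaplan-Meier, deaths censored: 1 − exp(−λ(1 − q)t)
- cumulative incidence of relapse: (1 − q)(1 − exp(−λt))

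For MRD-negative patients, λ = 0.6931/13 = 0.0533. At q = 0.2 and t = 24, the first gives 1 − exp(−1.024) = 64.1% and the second 0.8 × (1 − exp(−1.280)) = 57.7%. For MRD-positive patients, λ = 0.6931/8 = 0.0866, giving 1 − exp(−1.664) = 81.1% and 0.8 × (1 − exp(−2.079)) = 70.0%.

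24-month results (excess taken before rounding):

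| q | MRD−: 1−KM | MRD−: cum. inc. | Excess (points) | MRD+: 1−KM | MRD+: cum. inc. | Excess (points) |
|---|---|---|---|---|---|---|
| 10% | 68.4% | 65.0% | 3.4 | 84.6% | 78.7% | 5.9 |
| 20% | 64.1% | 57.7% | 6.3 | 81.1% | 70.0% | 11.1 |
| 30% | 59.2% | 50.5% | 8.6 | 76.7% | 61.2% | 15.4 |
| 40% | 53.6% | 43.3% | 10.3 | 71.3% | 52.5% | 18.8 |

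At q = 20% the apparent gap between MRD groups is 81.1 − 64.1 = 17.0 points by Kaplan-Meier and 70.0 − 57.7 = 12.3 points by cumulative incidence.

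**Step 2: time origin.** Simulation of 1,000 trials with n = 324, 25% MRD-positive, medians 13 and 8 months, q = 20%, and 59 + 12 months. The hazard ratio is the Peto estimate (MRD-positive against MRD-negative), with two-sided log-rank rejection at 0.05. Lead-ins from randomization to the MRD sample are assumed; for scale, Day 42 is about 42/30.4 = 1.4 months after treatment starts.

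| Lead-in MRD− / MRD+ (months) | HR from randomization | HR from MRD date | Rejection, randomization / MRD date |
|---|---|---|---|
| 1-1.5 / 1-1.5 | 1.76 | 1.76 | 89% / 89% |
| 1-2 / 1.25-2.25 | 1.71 | 1.76 | 86% / 89% |
| 1-1.5 / 1.5-3 | 1.58 | 1.76 | 76% / 89% |

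Keeping the randomization clock but using delayed entry at the sample also gives 1.76 in all three cases. The Peto estimate is an approximation and sits above the 13/8 = 1.625 built into the simulation, so the change between columns is the informative part. The rejection rates belong to n = 324, the Phase III-based size. Amendment 04 ends accrual, and the plan's Phase II-based marrow sample is 108.

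**The case against.** The strongest reply is that the plan already gives the competing-risk estimator to the quantity that needs it. TTR and relapse risk are named separately, and relapse risk gets cumulative incidence. Nowhere does the plan say that one minus the TTR curve will be reported as a relapse probability. A reader might infer that the substudy will publish two conflicting relapse figures, one of them biased; the documents do not support that. What stands is that two relapse summaries by MRD status are planned and nothing says which one is the probability.

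A reader might also infer that censoring deaths invalidates the MRD comparison. It does not. The log-rank test and Cox model with deaths censored compare the cause-specific hazard of relapse, which is a legitimate target. Gray's test addresses a different quantity and would not correct an error.

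Nor does the early origin add to the overstatement. Guaranteed relapse-free time lowers the curve at any fixed time from randomization. With a pooled median of 11.5 months, q = 20% and an assumed common lead-in of 1.5 months, one minus Kaplan-Meier at 24 months from randomization is 1 − exp(−0.0603 × 0.8 × 22.5) = 66%, against 69% if 24 months are counted from remission. The lead-in also applies to both groups, so it is not event-free time credited to one group alone.

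Adjustment for number of induction courses helps, but only in the multivariable models. The curves and the unadjusted log-rank test remain exposed. For RFS, Section 14.3.4 states no origin, so the same fault cannot be charged there.

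Finally, Section 14.3.2 lists these objectives as exploratory, and the Phase II-based versions are described as hypothesis-generating. That limits the importance of the point but does not remove it.

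**Conclusion.** The point holds in limited form. As defined, the TTR Kaplan-Meier curve is not an estimate of relapse probability. If read as one, it is too high at 24 months by about 3-10 points for MRD-negative and 6-19 points for MRD-positive patients. That range rests on the plan's medians, constant hazards, and an assumed 10-40% share of deaths without relapse; the documents give no such share.

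The clock starts before the grouping factor exists. The effect on the unadjusted MRD comparison is conditional: none with equal lead-ins, slight with a quarter-month difference, and a fall from 1.76 to 1.58 in the hazard ratio if MRD-positive patients are assessed clearly later. Those lead-ins are assumptions too. The concern would be greater if end-of-consolidation MRD were the factor, since patients must then have stayed relapse-free through consolidation.

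This is a minor improvement to an exploratory analysis. It has no bearing on the primary EFS or OS results.

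**What to change.** In Section 14.3.4:

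1. Make cumulative incidence, with death in remission as a competing event, the only estimate of relapse probability by MRD group. Drop the TTR Kaplan-Meier curve.
2. Keep the log-rank test and Cox model for relapse, labelled as comparisons of the cause-specific hazard. Gray's test is optional.
3. For end-of-induction MRD, start TTR, and OS when compared by MRD, at the MRD assessment. Alternatively, start at CR/CRi, as DFS does, with delayed entry at the MRD sample.
4. For end-of-consolidation MRD, use a landmark at that time point.

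The cost is a wording change and minor programming, since cumulative incidence is already planned. The one drawback is that TTR, and OS in these analyses, will have a different origin from the randomization-based endpoints, which table and figure footnotes should state.
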